### Design

For Aim 1, we plan to recruit 460 study participants from 19 memory care facilities. For the purpose of this study, facilities will include Skilled Nursing Facilities (SNFs), or equivalent. Aim 1 will be a randomized controlled study using a waitlist control group. The randomization will occur at the individual (resident) level within each facility to control for variations at each facility in terms of facility size, facility administration, and staff training. During the first 6 months, n=230 will receive the intervention (SafelyYou Guardian, i.e. real-time alarms through a phone call from the HIL to the facility, front line staff intervention, and OT review), and n=230 will not receive the intervention. This design is the most rigorous way to test the intervention against the control: the randomization allows for control of confounding variables and has been previously used in the evaluation of medications, non-pharmacological, and mobile electronic interventions (where use of placebo treatment and blinding is not feasible) [87-89]. Previous work used a baseline as control, allowing possible confounding variables. As we recognize that 50% of the interested participants will not receive the intervention, those residents will be offered the intervention for a 6-month extension period (in order to accomplish Aim 2). This is the best compromise between the need for a rigorous randomized controlled trial vs. ethical responsibility to maximize benefit to each study participant.

For Aim #2, we will measure response times to each fall and the amount of time a resident spends on the ground after each fall. We intend to include all 460 participants' data from Aim #1. These will be participants who receive the initial intervention (n=230) and the additional participants who are on the waitlist control group who will receive the intervention in the second 6month period. The design for Aim #2 is observational in nature. The significance is that a large cohort of video data about the naturalistic progression of falls in residents with dementia has never been conducted to our knowledge. We will determine if the two time variables (time to fall discovery by staff and time spent on the ground after a fall, controlling

for baseline participant characteristics – i.e., demographics and medical conditions) and facility size, will predict need for ER visits or hospitalizations.

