For aim #3, we will ascertain the occurrence of fall in the intervention group by doing follow-up case review of each detected fall. For the control group, we perform biweekly check with facility staff and family regarding knowledge and documentation of any falls. For falls in both the intervention and control group, we will additional collected data regarding occurrence of ED visit and hospitalization days. We will also include occurrence (or absence) of any operations, intensive care unit stays, and other medical procedures. We will also collect mortality data.

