#### **Data collection:**

Demographic and clinical data set: We collect demographic data including age, gender, race/ethnicity, primary clinical diagnoses for SNF stay with specific focus on dementia subtype, most recent orthopedic surgery (<3 months) or reason for hospitalization, chronic medical conditions (top 3), and baseline medications (number of medications). Beyond the data collected from the video, data specific to the falls is collected either by direct extraction from the platform or from incident reports kept by facilities as (State regulations require facility track and file incident reports for all known falls). For the control population, the time of unwitnessed falls is unknown, but the number of falls and ER visits is collected from the existing facility incident reports. For the population equipped with SafelyYou Guardian, we will have direct access to the time of the fall, the time it took the HIL to verify the fall and call the facility, and the time on the ground. Note that for the residents with SafelyYou Guardian, we expect these values to be in increments of minutes.

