#### Clinical outcomes.

For Aim #1, the primary outcomes are the number of falls detected by facilities using the adverse incident reporting system as per routine facility protocol. While use of video detected falls will be used in the intervention group to assist with prevention of future falls, we will not use this as the actual outcome measure: is not the standard-of-care, and the control group will not have video recorded outcomes. There is a bias for detecting falls using video since existing fall reporting systems do not capture falls which staff do not know about (e.g., when a resident is able to get back in bed after a fall). Staff-detected falls which automatically trigger adverse incident reporting is the “real-world” outcome measure and current stand-of-care. Thus, outcomes will differ by facility (each facility has different adverse incident reporting operations and implementation, hence the randomization at each facility will adjust for such variables).

Aim #2 will be a naturalistic observation of SafelyYou Guardian with HIL for 6 months. Specifically, for all the facilities, the use of the SafelyYou Guardian enables direct notification of falls to front-line staff in the facilities, by intervention of the HIL. We can directly measure time on the ground for the residents as follows: (1) The time of the fall is recorded by

SafelyYou Guardian (which detected it); (2) The time of intervention of the front-line staff is logged by the staff after finding the residents on the ground. This means that for the population with treatment, we can directly measure the time of fall discovery (successful call leading to front line staff intervention), and time on the ground (since time of the intervention is logged by the facility). This is because time on the ground for monitored residents can be measured precisely by video recording. Reduction of the time on the ground can be computed given the difference between the two.

Aim #3 will include number of ER visits and number of hospitalizations. We will obtain information about resident demographics, medical comorbidities, emergency room visits, and hospitalization data by asking the study participant legal representatives. In addition, we will have participant / participant Durable Power of Attorney complete HIPAA consent forms for release of medical records when indicated if the details of data are not available.

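### Only controls get a biweekly study enquiry about fall documentation, so the Aim 1 incident-report count may be ascertained differently by arm, with unknown net direction

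*Combined protocol and SAP*

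**What the plan says.** The Clinical outcomes section defines the Aim 1 outcome: "the primary outcomes are the number of falls detected by facilities using the adverse incident reporting system as per routine facility protocol". It justifies this choice over video counts: "Staff-detected falls which automatically trigger adverse incident reporting is the “real-world” outcome measure and current stand-of-care". The Data collection section gives the same source for controls: "the number of falls and ER visits is collected from the existing facility incident reports".

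The Aim 3 paragraph under Design sets a different fall follow-up in each arm. For the device arm, "we will ascertain the occurrence of fall in the intervention group by doing follow-up case review of each detected fall". For controls, "For the control group, we perform biweekly check with facility staff and family regarding knowledge and documentation of any falls". No periodic check is described for the intervention arm.

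Two further statements matter. Clinical outcomes acknowledges that "existing fall reporting systems do not capture falls which staff do not know about", and says of the intervention that "the use of the SafelyYou Guardian enables direct notification of falls to front-line staff in the facilities".

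**The concern.** Incident reports are a fair outcome if the same reporting process operates in both arms. A study contact every two weeks that asks staff and families of controls what they know and what has been documented is not part of routine reporting. It can prompt a late filing, or lead a family member to tell staff about a fall that then gets filed. Either adds to the control count of the primary outcome.

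The plan's safeguards do not reach this. Clinical outcomes relies on randomizing within each facility to deal with differences in reporting practice, and the Data analysis paragraph models nesting within centers. Both handle differences between facilities. A difference in prompting between arms inside a facility passes straight into the estimated treatment effect. The Design section also accepts that blinding is not feasible.

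**Working it through.** The plan gives no figure for how complete incident reporting is, or for how far a prompt or an alert changes it. There is no stated result to reproduce. The size can only be shown over an assumed range.

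**Inputs from the documents.** Monthly fall rate 0.49 (Data analysis). Target rate ratio 0.70, month-to-month correlation 0.8, 6 months of follow-up, 230 per arm and 10% dropout (sample-size text), so 230 × 0.90 = 207 per arm.

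**Assumed.** Two-sided 5% significance level (none is stated). Biweekly means every two weeks, so 26/2 = 13 checks per control in 6 months. g is the proportional gain in control reports and h the gain in intervention reports.

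**Step 1: the two arms side by side.**

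| | Control | Intervention |
|---|---|---|
| Periodic enquiry to staff and family | About 13 checks | None described |
| Event-triggered contact | None described | Alert to staff, then case review of each detected fall |
| Aim 1 source | Incident reports | Incident reports |
| Likely effect on reports | Up (g) | Up (h) |

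**Step 2: effect on the estimate.** Apparent rate ratio = true ratio × (1+h)/(1+g).

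| g | h | True 1.00 appears as | True 0.70 appears as |
|---|---|---|---|
| 5% | 0 | 1/1.05 = 0.95 | 0.67 |
| 10% | 0 | 1/1.10 = 0.91 | 0.64 |
| 20% | 0 | 1/1.20 = 0.83 | 0.58 |
| 10% | 10% | 1.00 | 0.70 |
| 20% | 10% | 1.10/1.20 = 0.92 | 0.64 |
| 10% | 20% | 1.20/1.10 = 1.09 | 0.76 |

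With h = 0, imitating the full 30% reduction would need g = 1/0.70 − 1 = 43%.

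**Step 3: chance of a significant false benefit, for h = 0 only.** Take SE² = (1/λ0 + 1/λ1) × f/n, with λ1 = 0.49, λ0 = 0.49(1+g) and n = 207. The factor f is (1 + 5 × 0.8)/6 = 0.833 under the plan's month correlation, or 1/6 if counts are pure Poisson over 6 months.

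For g = 10%: 1/0.539 + 1/0.49 = 3.896.
- f = 0.833: SE = 0.125, and ln(1.10)/SE = 0.0953/0.125 = 0.76. The probability is Φ(0.76 − 1.96) = 11.5%.
- f = 1/6: SE = 0.056, ratio 1.70. The probability is Φ(1.70 − 1.96) = 39.8%.

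The same steps give 5.8% and 13.6% for g = 5%, and 31.8% and 91.3% for g = 20%. The nominal value in this direction is 2.5%.

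**Step 4: after the fix.** If the check produces the same gain c in both arms and alerts add a gain d in the intervention arm, the factor is (1+c)(1+d)/(1+c) = 1+d, assuming the gains multiply. The check cancels and the alert effect stays. With d = 20%, a true 1.00 appears as 1.20 and a true 0.70 as 0.84.

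**The case against.** The strongest reply is that the check belongs to Aim 3, while Aim 1 is separately tied to routine incident reports. No text says that falls learned at the check are filed or counted. This stands in part: the link to the primary outcome is an inference. It is a short one, because the people asked about documentation include the staff of the facilities whose reports are counted, and no text keeps prompted reports out.

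Second, Data collection says State rules require a report for every known fall, and Clinical outcomes says staff detection triggers one automatically. If compliance were complete, a prompt could add reports only through falls that a family discloses to staff. This limits g but does not make it zero.

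Third, the intervention arm is not free of contact about falls. Staff are called about confirmed on-ground events, and each detected fall is reviewed. Those cues may be stronger than a biweekly question, and they raise h. This stands in full, and it is why the h = 0 rows cannot be read as the expected bias.

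Fourth, "The randomization will occur at the individual (resident) level within each facility", so both arms share a facility and its reporting system, and a question about controls may sharpen reporting for everyone. If half of a 10% gain spilled over, the ratio would be 1.05/1.10 = 0.95 rather than 0.91.

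A reader might infer that the control-only check will produce a false benefit. The documents do not support that: two mechanisms of unknown size act in opposite directions.

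**Conclusion.** Fall ascertainment differs between the arms, and the difference can reach the primary outcome. The control-only enquiry, taken alone, favors Hypothesis 1. Device alerts and case reviews work against it. The documents give neither g nor h, so neither the size nor the sign of the net bias can be stated.

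The size matters if the two gains differ: an unopposed 10% control gain would raise the false-benefit probability from 2.5% to between 11.5% and 39.8%. That range rests on the assumed gain, h = 0, a 5% two-sided test and the normal approximation. Opposing biases of unknown size cannot be relied on to cancel.

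The two asymmetries differ in kind. The alert is part of the intervention and cannot be removed. The enquiry is a study procedure and can be made equal. Once it is, the remaining mechanisms that the documents describe raise intervention reports, so an observed reduction would be easier to believe. The change should be made, but the point does not show that the primary comparison is invalid.

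**What to change.** 1. **Staff enquiry.** Make it one contact per facility, every two weeks, covering every enrolled resident with the same questions and form, without separating residents by arm. The contact already takes place, so the added cost is small.
2. **Family enquiry.** Use the same schedule in both arms, at a frequency the study can sustain. Extending the biweekly schedule to intervention families would add up to 230 × 13 = 2,990 contacts, which is not trivial. Asking all families every four weeks needs 460 × 6.5 = 2,990, the same total as biweekly contacts with control families alone. Dropping the check would be cheaper, but would remove the control fall ascertainment that Design sets for Aim 3.
3. **Aim 1 count.** State that study checks and case reviews do not create or amend incident reports, that reports are abstracted identically in both arms over the same 6 months, and that falls known only from a check or review are recorded separately and left out of the primary count.
4. **Flag prompted reports.** A facility may be obliged to file once it learns of a fall, so some prompted reports will occur. Record the fall date, filing date and study contact dates. Flag a report when the fall precedes a study contact and the filing follows it.
5. **Sensitivity analysis.** Repeat the Aim 1 model without flagged reports. Show exclusions for periodic checks and for case reviews separately as well as together, because case reviews occur in one arm only.
6. **Interpretation.** Acknowledge that staff alerts can still raise intervention-arm reports. The steps above do not remove that.

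Items 3 to 6 cost protocol and analysis-plan wording, a few date fields and one extra model run.

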#### Participant recruitment and retention

In the Phase I project, recruitment was performed by hosting a family night with care staff from the facility. Recruitment rate among families attending family nights was 85%. Our retention over 10 months with the 11 partner facility was near 100% (no family / resident ever requested to remove the system). One resident did begin taking the sign off the door after enrolling in the study, and the system was removed with approval from the family since he may have been attempting to object to the study. We credit this high retention to the very little burden required.

The recruitment of 460 residents will happen in batches (we expect to have access to our entire cohort 6 months from the start of the project). Once the resident population is recruited, we will deploy the system and onboard the facility staff. Onboarding will be gradual over 3 months. Through randomization, the population is split in half. One half, the control group, will not receive the intervention for the first 6 months, but will get the intervention for the next 6 months. The other half, the intervention group, will be in the study for the first 6 months only and then continue for the next 6 months. In total, 12 months will be needed per cohort. Installing the system requires 1-5 days depending on the facility size to mount the SafelyYou Guardian in the electrical closet alongside the router and PoE switches required to connect and power the cameras. Installation will be provided by SafelyYou contractor.

#### Subject Identification, Recruitment and Consent

All consent procedures will be conducted by the research study personnel or the facility memory care representative who often has a personal relationship with residents and families. At this time, the informed consent document will be explained in detail and any questions will be answered. All participants will have a documented cognitive impairment and designated Legally Authorized Representatives. Because the designated Legally Authorized Representatives is required for the individual to live in a memory care facility, no participants will have capacity to consent independently. Legally Authorized Representatives will instead provide consent. If the individuals with dementia express any desire not to participate verbally or non-verbally to facility staff or Legally Authorized Representatives, they are instructed to alert research study personnel to remove the participate from the study.. If at any time, residents express verbal or nonverbal indication that they would like the camera removed, facility staff are instructed to place a cover over the camera and alert research study personnel at [name] or [[contact]](mailto:[contact]) to remove the resident from the study. Camera covers are provided in advance with more available as needed.

Subjects will not be compensated for participation in this study.

Subjects will not be charged for any of the study activities.

Inclusion criteria: residents included for this study are residents of memory care facilities who have agreed to participate in this clinical trial. All pilots have been conducted based on study design approved by the UC Berkeley IRB and the California Department of Social

Services Community Care Licensing Division. We have not selectively recruited or excluded ethnic (or other) minorities.

Exclusion criteria: (1) residents about to be transferred to a different facility where higher level of care is needed; (2) residents unable to consent and without Legally Authorized Representatives to provide consent, and (3) residents with Legally Authorized Representatives that choose not to take part. Compensation and measures to reduced dropouts:

Drop out: We do expect some residents to move to another location or pass away and have included the expected dropout based on the Phase I project into the statistical calculations used below to determine the necessary participant number.

### **Study procedures**

After informed consent, each participant will be randomized to either standard-of-care (wait list control) vs. intervention. We will randomize participants within each facility as they are enrolled into the study. This ensures that site differences such as size, staff training, and other confounding variables will be controlled for by having a balanced number of intervention/control participants per site. Family meetings and staff education sessions will be conducted at each site.

If Legally Authorized Representatives wish to access recorded fall videos at any time, they can do so by contacting facility staff so they can walk through recorded video for the resident at the facility. These are sensitive videos, so we require Legally Authorized Representatives to visit the facility to view the videos with facility staff.

**Privacy and security safeguards.** Privacy: A common concern with any video-based monitoring system is privacy. Through the series of pilots discussed previously and shown in Fig. 3, we have systematically validated the privacy/safety tradeoffs for residents, families, staff, owners, and operators of memory care facilities. Pilot 2 demonstrated at small scale (one facility, 10 residents) that the industry would be receptive to video-based fall detection and prevention. Pilots 3 and 4 confirmed the approach with 11 facilities and 87 residents while demonstrating significant positive outcomes including 37% reduction in use of EMS for falls and 38% reduction in total falls. We now have paid commitments for 480 beds and ongoing discussions regarding expansion within the networks from the Phase I facilities, validating the benefits outweigh potential privacy and legal concerns for a number of families and providers. The combined benefits of (1) reduced time on the ground due to real-time intervention of front line staff, (2) immediate assessment of severity when a resident is found on the ground without witness, and (3) reduced likelihood of future falls through intervention of OT make our commercial approach viable. The key point is that as dementia progresses, the need to keep a loved one safe often surpasses concerns regarding their privacy. The benefits provided by SafelyYou in terms of reduced falls and ED visits have surpassed the concerns for the majority in memory care facilities where 85%-90% opt-in for the system. For more information from families and care staff validating these numbers and sentiments, please see letters from [name], [name], [name], [name], and video:

<https://youtu.be/ThUsBVOAJ3A>. This video was made with explicit permission from all residents/families for the purposes of promoting our work and supporting further recruitment. During pilots 2, 3 and 4, no live video was available and video was recorded whenever motion was detected. For new customers signing up for the system and for the Phase II clinical trial, no live video access is available and videos that do not contain a detected fall are not kept after 60 seconds as enabled by the highly accurate fall detection system developed in Phase I. We have never placed video cameras in bathrooms and will not for the Phase II clinical trial. In our 11 partner facilities, the Phase I showed that only 5-10% of

falls occur in the bathroom, and there is much good that can be done without needing the system in the bathroom. All study protocols have been approved by the UC Berkeley Committee for the Protection of Human Subjects. In all studies, privacy guidelines published by the California (CA) Department of Social Services (DSS) for video recording in private rooms

(<http://cclid.ca.gov/res/pdf/OfficeFunctions.pdf>) have been followed including signs on all doors to inform visitors and staff of video recording, no audio recording to avoid accidentally recording someone in a room which did not consent to recording, and signed privacy waivers are required from legal representatives. Care staff were further instructed to take down cameras if residents ever appeared to object. In a recent presentation of the Phase I results to California DSS which included the Deputy Director of the Department, explicit approval was granted by DSS to expand our operations in California. One representative from DSS commented that this should be required for dementia care; another confirmed that we are the only company operating this type of technology in California currently (since this was the first approval of this type given by DSS). We thus take several steps to provide privacy safeguards and believe that SafelyYou meets a critical unmet need for AD/DR care where safety concerns often surpass privacy concerns.

**Security:** SafelyYou relies on HIPAA compliant, state-of-the-art cybersecurity software and software architectures that protect against attacks/failures. AWS Cloud Security and local data encryption in motion and at-rest are used to prevent video being available to unauthorized users. See data management plan for details.

Recording: The recording process for the video proceeds as follows. A small, password-protected computer is placed in the facility and connected to each camera. Video will be recorded and stored on this small computer in an encrypted format. Recordings will be sent directly to SafelyYou through an encrypted channel after an event is detected and available to the facility staff through a password protected website hosted on Amazon Web Services.

Event Detection: As videos are recorded at the facility, the computer located in the facility will analyze the video streams and keep a buffer of 10 minutes of prior video from each camera. If a resident is detected on the ground or a resident is detected going from a laying position to a sitting position in bed, an alert will automatically be sent to the Magellan team, and the 10-minute buffer video will be uploaded. They will confirm a resident is on the ground by viewing a blurred version of the video as described above and reach out to the facility staff by phone or e-call system to inform them of the situation. The 10 minutes of video after a resident on the ground is confirmed will also be uploaded, enabling 20-minute window into how the fall occurred with minimal burden on the frontline care team. As long as an event such as a resident on the ground is detected, the system will continue to upload video in this way.

Abuse Reporting: Abuse reporting will be conducted following the requirements of the Welfare and Institutions (WIC) code. If any potential evidence of abuse is discovered, facility management will be immediately alerted. Note that evidence of abuse may be missed by the SafelyYou system since only video of detected events is uploaded. The SafelyYou system is not meant to be a system for reporting abuse; it is meant to be a system for improving fall prevention practices in memory care. The research system is not intended to screen for abuse or theft suspicions. As discussed below, only video of detected events are available. It is thus very possible that incidents of abuse or theft are never uploaded for viewing by facility personnel.

Confidentiality: Study data will be handled as confidentially as possible. If results of this study are published or presented, individual names and other personally identifiable

information will not be used unless you give explicit permission for this in the separate media release form.

To minimize the risks to confidentiality, we will do the following:

- During data collection, all data will be transmitted over a secure channel.
- Research records, including video recordings and computer-based data, will be stored in an encrypted format, on a password-protected computer in a physically secure room.
- Study data will be kept confidential, unless it is certain information that it must be reported for legal or ethical reasons, such as child abuse, elder abuse, intent to hurt self or others. We use the term elder abuse as defined by California Law in the Welfare and Institutions (WIC) code.

The research data will be maintained for possible use in future research. We will retain this data for up to 5 years after the study is over at which point it will be deleted. It is retained for 5 years to ensure sufficient time is given to study the content within the data and publish the results. It will not be used for any purpose beyond what is described here without explicit approval. Use of the study data will be restricted to SafelyYou research study personnel and their collaborators. For instance, if medically relevant information is observed such as significant patterns in fall behavior, we may ask primary care physician or medical collaborators from the UCSF Memory and Aging Center to provide additional clinical consultation. The same measures described above will be taken to protect confidentiality of this study data.

